6.2.7 Missing Diagnosis Dates

If the month and year are present but the day is missing, the diagnosis date will be set to first day of the relevant month. If only the year is recorded the diagnosis date will be set as "01-Jan" for that year.

6.2.8 Exposure to Study Drug

Total volume of bryostatin infused (mg) during the study will be calculated as:

$$\sum_i [0.024 \cdot L_i + 0.020 \cdot (1 - L_i)] \cdot \left[C_i + (1 - C_i) \cdot \frac{TVI_i}{59.6 \cdot L_i + 58.0 \cdot (1 - L_i)} \right] \quad \text{Eq 2}$$

0.024 (mg) – loading dose of bryostatin, 0.020 (mg) – maintenance dose of bryostatin, according to Section 4.1 of the Protocol,

59.6 (mL) – total solution volume for loading dose, 58.0 (mL) – total solution volume for maintenance dose, according to Section 5.3 of the Protocol,

L_i – sign for loading dose, equals to 1 if dose is loading and equals to 0 if dose is maintenance,

C_i – sign for completed dose, equals to 1 if subject received the full intended infusion and equals to 0 otherwise,

TVI_i – total volume infused (mL), in case of incomplete infusion

i – number of an infusion. The sum should be calculated for all performed infusions.

Planned dose of bryostatin is the sum of doses of full infusions for whole study: for each of 2 courses there are 2 infusions of loading dose 24 mcg and 5 infusions of maintenance dose 20 mcg. Totally planned dose equals to $2 \cdot (2 \cdot 54 + 5 \cdot 20) = 416$ mcg.

This value will be used for calculation of fraction of subjects received at least 80% of planned dose.

QMD Ref: Worldwide-TMP-ST-005-7.0 Effective: 12Aug2019	Governing QMD: Worldwide-SOP-ST-001
Confidentiality Statement	
This document is the property of Worldwide Clinical Trials Inc. and may not be duplicated, copied, altered or removed from company without prior approval from Worldwide Quality Assurance or in compliance with Worldwide Standard Operating Procedures.	

Worldwide Clinical Trials Controlled Quality Management Document		
 WORLDWIDE CLINICAL TRIALS	Sponsor:	Synaptogenix, Inc.
	Protocol Number:	NTRP-101-204
STATISTICAL ANALYSIS PLAN. PHASE 2-3-4		

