4.1 Dose Rationale

The primary objective of treatment for cognitive disorders with bryostatin is activation of PKC ϵ , not downregulation as was attempted for the oncology indications. Bryostatin activation of PKC ϵ is dose dependent, where lower doses activate PKC ϵ and increase de-novo synthesis of the enzyme, while higher doses of bryostatin downregulate PKC ϵ .

The dosing regimen is based on the recently completed phase 2 study, NTRP101-202, in which the safety and efficacy analyses indicated a clear advantage of the 20 μ g dose over the 40 μ g dose.

The oncology data suggest that the dose-limiting side effect of myalgia is dose dependent and cumulative and likely related to the down regulation of PKC ϵ . This was not seen in the NTRP101-201 study, in which there were no reports of myalgia after a single 25 μ g/m² dose of bryostatin was administered, nor in the recently completed NTRP101-202 study, in which myalgia was considered an adverse event of special interest. In NTRP101-202, in which subjects received 7 doses of study drug, myalgia was seen in 5 subjects; 4 of those subjects were given the higher 40 μ g dose of bryostatin. Myalgia observed was mostly mild and managed with analgesics.

Dosing in this study will begin with two initial loading doses at one-week intervals that are 20% higher than the maintenance dose (i.e., 24 μ g) to assure enzyme activation. Dosing will then continue with 20 μ g administered every other week for 5 weeks, for a total of 7 doses. The first treatment period will occur over 15 weeks, including a follow-up visit 30 days after the last dose. The same treatment regimen will be administered for subjects who qualify for a second course of treatment. The total study drug administered to a particular subject is 14 doses.

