5.0 Bryostatin

The investigational drug product, bryostatin, is a sterile, pyrogen-free, lyophilized powder intended for IV infusion upon reconstitution and dilution. Bryostatin will be supplied in a 10 mL vial containing 0.025mg bryostatin, 2.5 mg povidone lyophilized from 40% t-butanol. Accompanying each vial of bryostatin will be a 10mL vial containing 2mL of sterile PET diluent [60% v/v polyethylene glycol 400, 30% v/v dehydrated ethyl alcohol, and 10% v/v Tween-80 (polysorbate 80)].

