6.9 Exposure to Study Drug

Data on exposure will be presented by randomized treatment group, overall, and by visit/whole study for the Safety Analysis Set. Following parameters will be presented in a table:

- For each visit:
 - Subjects who had an infusion
 - Subjects that received full infusion
 - Subjects that had at least 1 interruption
 - Subjects that received partial infusion
- For whole study

QMD Ref: Worldwide-TMP-ST-005-7.0 Effective: 12Aug2019	Governing QMD: Worldwide-SOP-ST-001
Confidentiality Statement	
This document is the property of Worldwide Clinical Trials Inc. and may not be duplicated, copied, altered or removed from company without prior approval from Worldwide Quality Assurance or in compliance with Worldwide Standard Operating Procedures.	

Worldwide Clinical Trials Controlled Quality Management Document		
 WORLDWIDE CLINICAL TRIALS	Sponsor:	Synaptogenix, Inc.
	Protocol Number:	NTRP-101-204
STATISTICAL ANALYSIS PLAN. PHASE 2-3-4		

- Subjects that received all full infusions
- Subjects that had at least 1 interruption
- Subjects that received at least 1 partial infusion
- Subjects who received 1 unfusion, ≥ 2 infusion and so on.
- Total volume of bryostatin infused
- Subjects who had $\geq 80\%$ of planned dose

All data on exposure will also be listed.

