6.10 Treatment Compliance

Number and percentage of subjects receiving at least 80% of planned dose will be presented.

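### SAP 6.2.8 computes the planned dose with 54 instead of the 24 mcg loading dose (416 instead of 296 mcg), so the descriptive line for subjects at or above 80% of planned dose would read 0%

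*SAP*

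**What the plan says.** SAP 6.2.8 defines two quantities. Eq 2 adds up the bryostatin a subject received, crediting 0.024 mg for a full loading infusion, 0.020 mg for a full maintenance infusion, and a volume-based fraction for an incomplete one. The planned dose is then defined as the sum of full infusions over the whole study. For each of the two courses, "there are 2 infusions of loading dose 24 mcg and 5 infusions of maintenance dose 20 mcg". The evaluation that follows reads: "Totally planned dose equals to $2 \cdot (2 \cdot 54 + 5 \cdot 20) = 416$ mcg".

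The figure has a stated use: "This value will be used for calculation of fraction of subjects received at least 80% of planned dose". That fraction appears in two places. SAP 6.9 lists it among the whole-study exposure items ("Data on exposure will be presented by randomized treatment group, overall, and by visit/whole study for the Safety Analysis Set"), and it is all that SAP 6.10 specifies: "Number and percentage of subjects receiving at least 80% of planned dose will be presented".

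Protocol 4.1 describes "two initial loading doses at one-week intervals that are 20% higher than the maintenance dose", with 20 mcg as the maintenance dose and 24 mcg given as the loading dose. It adds: "The total study drug administered to a particular subject is 14 doses".

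**The concern.** The planned-dose expression uses 54 where the sentence before it says 24, and the wrong number carries through to the total. Numerator and denominator of the compliance fraction then rest on different loading doses: Eq 2 credits 24 mcg, while the planned dose assumes 54. If the denominator exceeds what a fully dosed patient can receive by enough, nobody reaches 80%. The line then no longer separates adherent from non-adherent patients, and the study report would misstate compliance.

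**Working it through.** **Inputs**
- Loading dose 24 mcg, maintenance dose 20 mcg; 2 loading and 5 maintenance infusions per course; 2 courses (SAP 6.2.8 text and Eq 2; Protocol 4.1).
- 14 doses in total (Protocol 4.1).
- Vial content 25 mcg (Protocol 5.0: "Bryostatin will be supplied in a 10 mL vial containing 0.025mg bryostatin"), made up with 1 mL diluent and 9 mL saline to 10 mL; 9.6 mL drawn for a loading dose and 8.0 mL for a maintenance dose (Protocol 5.3).

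**The SAP's own figure**

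2 × (2×54 + 5×20) = 2 × (108 + 100) = 416 mcg. This reproduces exactly, but only with 54. It cannot be obtained from 24, so a misread character in the PDF does not explain it: expression and result agree with each other on the wrong input.

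**Which loading dose is right**

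The concentration is 25 mcg / 10 mL = 2.5 mcg/mL. Loading: 9.6 × 2.5 = 24 mcg. Maintenance: 8.0 × 2.5 = 20 mcg. The preparation instructions therefore confirm 24 independently of the dose text. One 25 mcg vial could not supply 54 mcg.

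**Correct planned dose**

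2 × (2×24 + 5×20) = 2 × (48 + 100) = 296 mcg. This equals the most Eq 2 can credit for the 14 scheduled infusions: 4×24 + 10×20 = 296 mcg.

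**Effect on the 80% line**
- Full dosing over the SAP's denominator: 296/416 = 71.2%.
- Threshold as written: 0.8 × 416 = 332.8 mcg, and 332.8/296 = 112.4% of the full schedule.
- Threshold when corrected: 0.8 × 296 = 236.8 mcg.

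The table takes all other infusions as complete. The ranges run from only loading doses missed to only maintenance doses missed.

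| Full infusions missed | Received (mcg) | % of 296 | % of 416 |
|---|---|---|---|
| 0 | 296 | 100 | 71.2 |
| 2 | 248 to 256 | 83.8 to 86.5 | 59.6 to 61.5 |
| 3 | 224 to 236 | 75.7 to 79.7 | 53.8 to 56.7 |

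With 296, missing any two passes and missing any three fails. With 416, every row fails, including the first.

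**Placebo arm.** The result is the same. If Eq 2 is applied nominally to placebo infusions, the maximum is again 296 mcg. If their bryostatin dose is taken as zero, the fraction is zero.

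**Reach.** The per-protocol rule in SAP 6.1.3 counts missed doses, not micrograms. The full Analysis Set and Completer Analysis Set do not use cumulative dose. The other exposure items in SAP 6.9 (full, partial and interrupted infusions, number of infusions, total bryostatin infused) do not divide by 416.

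**The case against.** The best reply is that the SAP defines the planned dose correctly in words just before mis-evaluating it, so a programmer who works from the definition gets 296. If 416 were hard-coded, a 0% line in both arms would sit beside counts of subjects who received all full infusions and would contradict them. The exposure table is also marked IP in the SAP's validation column, so someone would probably notice. Nothing inferential depends on the figure.

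Most of this stands. The 0% outcome is conditional on following the line as written, the error would show itself in the output, and the effect is confined to one descriptive percentage. But the SAP does not leave the value as an illustration: it instructs that this value be used. Programmers working from the same specification could carry the same wrong constant. If one of them corrects it silently, the output departs from the approved plan with no record. Neither outcome is better than correcting the line now.

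One could also say that Protocol 4.1 describes 14 doses as the schedule and does not state it as a limit. That is fair, but reaching 332.8 mcg would take a further 36.8 mcg, which is 36.8/20 = 1.84 maintenance infusions, so two extra infusions in practice. No patient dosed to protocol gets there.

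**Conclusion.** The concern holds: the figure is wrong as written, and the plan puts it to use. The planned dose is overstated by 416 − 296 = 120 mcg, and the 80% threshold stands at 332.8 mcg instead of 236.8 mcg, above anything a protocol-dosed patient can receive. The compliance line would report 0% for both arms, on two assumptions: that 416 is programmed as stated, and that no subject receives more than the 14 scheduled infusions. The arithmetic is certain and the consequence narrow. It should be fixed because it defeats the only output SAP 6.10 specifies; the trial's efficacy and safety conclusions do not depend on it.

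**What to change.** In SAP 6.2.8 replace 54 with 24 and 416 with 296 mcg. Give the total also as 0.296 mg, the unit of Eq 2, and state the resulting threshold of 236.8 mcg. That is one corrected line, with no protocol amendment, no IRB resubmission and no site action.

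A separate and minor point can be settled in the same revision. SAP 6.1.3 treats three or more missed doses as a major deviation, so at least 12 of 14 are needed (85.7%). Protocol 9.1 asks for at least 11 of 14, which is 78.6% although it is labelled 80%. The SAP takes precedence and the per-protocol set is only supportive, so an entry in SAP section 9 recording the change is enough. If the sponsor meant to keep 11 of 14, SAP 6.1.3 should be reworded instead. The dose correction does not depend on this choice.

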6.1.4 Safety Analysis Set

The Safety Analysis Set (SAS) is defined as all randomized subjects who received any study medication (either partial or completed infusions of bryostatin or placebo).

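### SAP 6.2.8 sets the planned dose at 416 mcg instead of 296 mcg, so even a fully dosed subject scores 71.2% and cannot meet the 80% compliance threshold

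*SAP*

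**What the plan says.** SAP 6.2.8 defines the amount of bryostatin infused (Eq 2, in mg). Each infusion contributes 0.024 mg if it is a loading dose and 0.020 mg if it is a maintenance dose, scaled down by volume when incomplete. On scope it says: "The sum should be calculated for all performed infusions". The only indicators in the formula are for loading dose and completion.

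The same section then describes the plan in words, "for each of 2 courses there are 2 infusions of loading dose 24 mcg and 5 infusions of maintenance dose 20 mcg", and follows this with the total: "Totally planned dose equals to $2 \cdot (2 \cdot 54 + 5 \cdot 20) = 416$ mcg". On its use it says: "This value will be used for calculation of fraction of subjects received at least 80% of planned dose".

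That fraction appears twice. It is a whole-study row in SAP 6.9, where "Data on exposure will be presented by randomized treatment group, overall, and by visit/whole study for the Safety Analysis Set". It is also the sole content of SAP 6.10: "Number and percentage of subjects receiving at least 80% of planned dose will be presented". The Safety Analysis Set (SAP 6.1.4) includes placebo recipients.

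Protocol 4.1 agrees with the wording and not with the sum: the loading dose is 24 µg, the maintenance dose is 20 µg, and "The total study drug administered to a particular subject is 14 doses". Protocol 5.1 gives the bryostatin content of a placebo vial as 0.0 mg. The treatment label prescribed in SAP 6.3 gives the active dose as 0.20 mg. SAP section 9, which lists changes to the planned analysis, touches none of this.

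**The concern.** The planned dose is the denominator of the compliance proportion, and the SAP tells the programmer which number to use. If that number exceeds the largest dose the schedule allows by enough, the proportion is fixed at zero however well the trial was dosed. A reader of the study report would then see no compliant subjects in either arm, in a trial whose infusions are given under clinical supervision.

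Two related points affect the same table:

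- Eq 2 is described as bryostatin infused but does not depend on treatment. Applied to everyone in the Safety Analysis Set, it would show drug in the placebo column and inflate the overall column.
- The 0.20 mg arm label misstates the dose wherever it is printed.

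**Working it through.** **Inputs**

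- Courses: 2. Infusions per course: 2 loading and 5 maintenance (SAP 6.2.8; 14 in total, Protocol 4.1).
- Loading dose 24 mcg, maintenance dose 20 mcg (SAP 6.2.8 text, Eq 2 constants, Protocol 4.1).
- Printed planned dose: 416 mcg. Threshold: 80%.

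**1. Reproduce the printed figure**

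2 × (2 × 54 + 5 × 20) = 2 × 208 = 416 mcg. The expression and its result agree, so the 54 is not a character misread from the PDF. A small search over loading terms 20, 24, 25, 54, 58 and 59.6 and maintenance terms 20, 24, 25 and 58 found only 54 with 20 giving 416.

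**2. Correct figure from the SAP's own doses**

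2 × (2 × 24 + 5 × 20) = 2 × 148 = 296 mcg.

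Overstatement: 4 × (54 − 24) = 120 mcg, and 120/296 = 40.5%.

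**3. Eq 2 for a fully dosed subject**

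4 × 0.024 + 10 × 0.020 = 0.296 mg = 296 mcg.

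**4. Effect on the 80% row**

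| | As printed | Corrected |
|---|---|---|
| Planned dose | 416 mcg | 296 mcg |
| 80% cut-off | 332.8 mcg | 236.8 mcg |
| Fully dosed subject | 296/416 = 71.2% | 296/296 = 100% |
| Meets 80%? | No | Yes |

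Since 332.8 exceeds 296, no subject on the planned schedule can qualify as printed.

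**5. Does the corrected cut-off behave sensibly?** (whole infusions only)

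- At most 2 missed doses: at least 296 − 2 × 24 = 248 mcg, 248/296 = 83.8%, pass.
- 3 or more missed doses: at most 296 − 3 × 20 = 236 mcg, 236/296 = 79.7%, fail.

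This is the same split as the missed-dose criterion in SAP 6.1.3. It differs by one dose from Protocol 9.1, which admits subjects with 11 of 14 doses to the per-protocol set: 11 whole infusions give at most 236 mcg and fall just short of 236.8.

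**6. Placebo row**

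Eq 2 read literally for a placebo subject with 14 full infusions gives 0.296 mg, against a true value of 14 × 0.0 = 0 mg.

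**7. Label**

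20 µg = 0.020 mg, and 0.20/0.020 = 10.

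**The case against.** The strongest reply is that this is one typing slip in a descriptive denominator and is easy to catch. The right doses stand in the sentence before it and in Eq 2, and a zero count would clash with neighbouring rows. SAP 6.9 also tabulates full, partial and interrupted infusions and the number of infusions received. None of these uses 416, so the dosing pattern would still be visible. That is fair and it limits the harm, but 416 is still the value the SAP instructs the programmer to use.

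Two qualifications on the consequence also stand. The SAP never names Eq 2 as the numerator, and the 71.2% assumes mg are converted to mcg. Under the display rule in SAP 6.3, a zero row would print a count of 0 without a percentage. The first is an assumption to state, though no other dose total is defined. The second concerns format only.

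On the placebo row, one can argue that bryostatin infused is zero for placebo by definition, and that a treatment-free formula is what makes a compliance measure possible in both arms. Both arguments have force. The table shell is not in the documents, so whether placebo subjects would be credited with drug depends on the programming. The point is best read as a needed clarification. The label is a proofreading matter that enters no calculation.

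**Conclusion.** The concern holds, at minor severity. The planned dose should be 296 mcg; the printed 416 mcg is 40.5% too high. Taking Eq 2 as the numerator and converting units, the compliance rows in SAP 6.9 and 6.10 would count no subjects in either arm as written. Corrected, they would count every fully dosed subject.

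The placebo-column error (0.296 mg against 0) arises only if Eq 2 is programmed literally for all treated subjects. The arm label is wrong by a factor of 10.

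Nothing inferential depends on any of this. The efficacy analyses and adverse-event counts do not use the planned dose, and the per-protocol set is defined by missed doses.

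**What to change.** - In SAP 6.2.8, replace 54 with 24 and 416 with 296 mcg, giving an 80% cut-off of 236.8 mcg. This alone cures the main error.
- For the 80% rows in 6.9 and 6.10, state that the numerator is Eq 2 expressed in mcg, applied in both arms and labelled as nominal assigned dose. Compliance then stays comparable between bryostatin and placebo.
- Report the mass of bryostatin infused only for subjects who received bryostatin, with no placebo or overall value.
- In SAP 6.3, change the active-arm label to 20 µg.

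The cost is a few lines of the SAP and the matching shell for Table 14.3.5.1: one constant, one row label, one row restriction and one arm label. The mass row loses the overall column that 6.9 now implies. No data collection or efficacy programming changes.

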6.2.9 Inexact Values

In the case where a variable is recorded as “> x”, “≥ x”, “< x” or “≤ x”, a value of x will be taken for analysis purposes.

6.2.10 Electrocardiogram Data

For ECG data recorded on continuous scales, if more than one value is recorded at a time point, the mean value rounded to the integer will be presented. For overall interpretation if more than one value is recorded, the most severe (worst case) of the respective readings will be taken.

6.2.11 Columbia-Suicide Severity Rating Scale (C-SSRS)

The following outcomes are C-SSRS categories and have binary responses (yes / no). The categories have been re-ordered from the actual scale to facilitate the definition of composite endpoints:

Category 1	Wish to be Dead
Category 2	Non-specific Active Suicidal Thoughts
Category 3	Active Suicidal Ideation with Any Methods (Not Plan) without Intent to Act
Category 4	Active Suicidal Ideation with Some Intent to Act, without Specific Plan
Category 5	Active Suicidal Ideation with Specific Plan and Intent
Category 6	Preparatory Acts or Behavior
Category 7	Aborted Attempt
Category 8	Interrupted Attempt
Category 9	Actual Attempt (non fatal)
Category 10	Completed Suicide

Suicidal Ideation since baseline – A “yes” answer at any time during double blind treatment to any one of the 5 suicidal ideation questions (categories 1-5) on the C-SSRS.

QMD Ref: Worldwide-TMP-ST-005-7.0 Effective: 12Aug2019	Governing QMD: Worldwide-SOP-ST-001
Confidentiality Statement	
This document is the property of Worldwide Clinical Trials Inc. and may not be duplicated, copied, altered or removed from company without prior approval from Worldwide Quality Assurance or in compliance with Worldwide Standard Operating Procedures.	

Suicidal Behavior since baseline – A “yes” answer at any time during double blind treatment to any one of the 5 suicidal behavior questions (categories 6-10) on the C-SSRS.

There will be no imputation of missing data for C-SSRS.

6.2.12 Unscheduled Visits

Only scheduled post-baseline laboratory, electrocardiogram, physical examination, and vital signs values will be tabulated. Post-baseline repeat / unscheduled assessments will only be listed in the relevant appendices to the CSR.

6.3 Conventions

All data listings, summaries, figures, and statistical analyses will be generated using SAS version 9.3 or higher¹.

Summaries will be presented by treatment group for efficacy endpoints and overall. Treatment group labels will be displayed as follows:

Bryostatin (0.20 mg)	Placebo
-------------------------	---------

Overall columns are to be included within the table shells as follows:

Parameters	Columns
Demography	Treatment and overall
Baseline	Treatment and overall
Disposition	Treatment and overall
Efficacy	Treatment
AEs	Treatment
Other safety	Treatment

Listings will be sorted in the following order: treatment group, subject, parameter, and visit unless otherwise stated. All data will be listed, subjects who were not randomized will be displayed after the randomized treatment groups.

Worldwide Clinical Trials Controlled Quality Management Document		
 WORLDWIDE CLINICAL TRIALS	Sponsor:	Synaptogenix, Inc.
	Protocol Number:	NTRP-101-204
STATISTICAL ANALYSIS PLAN. PHASE 2-3-4		

Continuous variables will be summarized by the number of non-missing observations, mean, median, inter-quartile range, standard deviation, and minimum and maximum.

Categorical variables will be summarized by presenting the frequency and percent. Percentages will be based on the number of non-missing observations or the subject population unless otherwise specified. For each variable, all categories will be shown. Zero frequencies (but not the percent) within a category will be presented.

